3.2 Endpoints

Primary Effectiveness Endpoint:

Mean anterior myocardial infarct size (IS), as determined by Cardiac Magnetic Resonance (cMR) imaging at 4-6 days post infarct in the Test Arm (cooling + PCI) compared to the Control Arm (PCI only). Infarction Size (IS) is defined as % Left Ventricular Mass as measured by Cardiac Magnetic Resonance (cMR) imaging. Infarct Size (IS) will be assessed by Cardiac Magnetic Resonance (cMR) at 4 – 6 days following the index procedure.

Primary Safety Endpoint:

Per-patient rate of composite Major Adverse Cardiac Events (MACE) subjects, defined as Cardiac Death (CD), All Myocardial Infarction (all MI) and Clinically-Indicated Target Vessel Revascularization (CI-TVR) at 30 days; non-inferiority to the control.

Additional Safety Endpoints:

The following clinical components of MACE will be evaluated for per-patient rate at 30 days:

- Death (Cardiac, Vascular, Non-Cardiovascular)
- Myocardial Infarction (MI)
 - Attributable to target vessel (TV-MI)
 - Not attributable to target vessel (NTV-MI)
- Target Vessel Revascularization (TVR)
 - Clinically-indicated TVR
 - Not clinically-indicated TVR
- All coronary revascularization
- Stent Thrombosis
 - Timing (Acute, Sub-acute)
 - Evidence (Definite and Probable)

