An enrolment of 500 would be able to demonstrate 91% power and 95% 1-sided significance with alpha=0.05. The safety endpoint will be considered to have been met if there is a high posterior probability of non-inferiority [i.e. $P(\pi_t < \pi_c + 6\%) > 95\%$]. With 20% dropout, the power becomes 86%.

6 General Considerations

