6.2 Analysis Populations

The Intention-to-Treat (ITT) analysis set will be used for primary efficacy statistical analyses and summaries. The ITT population includes subjects who have signed an informed consent and have been randomized to the Test Arm or the Control Arm of the trial. ITT subjects will be evaluated according to the group to which they were randomized.

The Per-Protocol (PP) analysis set will also be evaluated. The PP population includes those subjects who met all inclusion and exclusion criteria, were randomized to either the Test or Control arm, received the treatment to which they were randomized, and complied substantially with the treatment timeline and steps of this protocol without major protocol violations.

The Safety Analysis Set, which includes all ITT subjects, will be used to evaluate safety endpoints. For the safety analysis, subjects will be followed for all adverse events for 12 months post procedure. Additionally, all subjects in this set will be confirmed as followed for 12 months for the incidence of Adverse Events, Serious Adverse Events (SAEs), Death and Heart Failure (as assessed by NYHA and Kansas City Cardiomyopathy Questionnaire (KCCQ), as applicable).

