6.7 Multiple Testing

For this trial, there is only one primary effectiveness outcome with two interim analyses. Overall significance value is preserved for interim analyses with established stopping rules preserving the overall type 1 error rate of alpha for <0.05.

For primary and secondary safety analyses, given the number of statistical tests, adjustment for multiplicity is considered counterproductive for considerations of safety as there is no control of the type I error for a single hypothesis. Tests will be conducted using one-sided test at alpha 0.05 level of significance.

All other analyses will be conducted using two-sided tests at the alpha=0.05 level of significance.

7 Summary of Study Data

[figure not shown]
Data will be sorted by treatment and centre and structured with columns for Test and Control. Descriptive and efficacy figures and tables will be produced for ITT and PP population. All

continuous variables will be summarised using the following descriptive statistics: n (non-missing sample size), mean, standard deviation, median, maximum and minimum. The frequency and percentages (based on the non-missing sample size) of observed levels will be reported for all categorical measures. In general, all tables will be annotated with population size relevant to the table/treatment, including any missing observations.

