8.1 Primary Efficacy Analysis

To evaluate anterior infarct size (%LV) in Control and Treatment Arm, summary statistics will be used; n, mean, standard deviation median, interquartile range, minimum, maximum will be reported. T-test (2-sided) or Wilcoxon rank-sum test (2-sided) will be used as appropriate to calculate p-value after evaluation for normality.

9 Safety Analyses

To summarize incidence of adverse events, summary for all site reported events will be conducted on patient basis on the safety analysis set. Specifically, each patient will be counted once for an event and any repetitions will be ignored; the denominator will be the sample population size. Summaries will be produced by treatment (Test vs. Control) as well as an “All Patients” column. 1-sided Chi-square test or Fisher’s-exact test will be used as appropriate depending on whether number of patients are fewer than 5, in which case Fisher’s exact test will be used.

Only deviations from the aforementioned analytical and summary approaches will be noted in the subsequent subsections of section 9.

The only summarized variable is MACE, which is also a composite endpoint.

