9.1 Adverse Events

The summary statistics will be produced in accordance with section 7. When calculating the incidence of adverse events, or any sub-classification thereof by treatment each subject will only be counted once and any repetitions of adverse events will be ignored; the denominator will be the total

population size. Incidence of specific AEs will be presented in summary form up to 30 days. For 12 months follow up, all AEs incidences will be summarized.

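### The plan gives conflicting denominators for 30-day MACE; the Section 9 rule counts subjects lost before day 30 as event-free, which, unless loss falls mainly on Control, favours non-inferiority

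*SAP*

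**What the plan says.** The primary safety endpoint in SAP Section 3.2 is the "Per-patient rate of composite Major Adverse Cardiac Events (MACE) subjects" at 30 days, tested for non-inferiority. Sections 3.1 and 5 set the margin at 6 percentage points.

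The SAP points to two different denominators:

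- **Whole set.** Section 9 counts each patient once per event on the safety analysis set and adds that "the denominator will be the sample population size". Section 9.1 repeats the rule for adverse events: "any repetitions of adverse events will be ignored; the denominator will be the total" population size. Section 6.2 defines the set: "The Safety Analysis Set, which includes all ITT subjects, will be used to evaluate safety endpoints". Section 9 says that later subsections note only departures from its approach, and it names MACE: "The only summarized variable is MACE, which is also a composite endpoint". None of Sections 9.1 to 9.4 gives MACE another denominator.
- **Subjects with data.** Section 7, to which Sections 9.1 and 9.2 refer for their summary statistics, says: "The frequency and percentages (based on the non-missing sample size) of observed levels will be reported for all categorical measures". Section 5 states, for the safety endpoint, "With 20% dropout, the power becomes 86"%, down from 91%. That fall makes sense only if lost subjects leave the analysis.

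Section 6.4 decides on imputation for the primary effectiveness analysis only. No section says how a subject with unknown 30-day MACE status enters the safety analysis.

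**The concern.** If the whole safety set is the denominator and lost subjects contribute no event, each arm's observed rate is roughly the true rate times (1 − loss). With equal loss the difference shrinks by the same factor, while the margin stays at 6 points. In a superiority comparison this dilution would be conservative. In a non-inferiority comparison it makes a claim of safety easier to reach.

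The conflict also matters apart from any bias. Two programmers following this SAP, one from Section 7 and one from Section 9, could report different rates and different decisions for the primary safety endpoint.

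**Working it through.** **Inputs.** Control MACE 6.6%, treatment 7.5%, alternative control rate 7%, margin 6 points, one-sided alpha 0.05, 500 subjects, 20% drop-out (all Section 5); 1:1 allocation (Section 4.1), so 250 per arm.

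**1. The plan's own power figures.** Normal approximation with unpooled variance:

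power = Φ[(0.06 − (pT − pC))/SE − 1.645], SE = √{[pC(1 − pC) + pT(1 − pT)]/n}.

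| Rates | n = 250 per arm | n = 200 per arm |
|---|---|---|
| Control 6.6%, Test 7.5% (as stated) | 72.0% | 63.6% |
| Control 7.5%, Test 6.6% (swapped) | 91.5% | 85.3% |

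The stated 91% and 86% are approached only with the two rates swapped. That is a separate matter. What counts here is that the second figure corresponds to 200 per arm, so Section 5 takes lost subjects out of the denominator. Had it kept 250 and counted them as event-free, the swapped rates would become 6.0% and 5.28%, SE = 0.02063, and power would rise to Φ(0.0672/0.02063 − 1.645) = 94.7% instead of falling.

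**2. Effect of the Section 9 rule.** Assume a true excess of exactly 6 points, non-informative loss d equal in both arms and before day 30, and none of the lost subjects' events recorded. Worked case, d = 20%, control 6.6%:

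- Control 0.8 × 6.6% = 5.28%; Test 0.8 × 12.6% = 10.08%; apparent difference 4.8 points.
- SE = √[(0.0528 × 0.9472 + 0.1008 × 0.8992)/250] = 0.0237.
- False non-inferiority = Φ[(0.06 − 0.048)/0.0237 − 1.645] = Φ(−1.139) = 12.7%.

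Results at 250 per arm, control rate 6.6% to 7%:

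| Equal loss before day 30 | Normal approximation | Exact enumeration, unpooled test |
|---|---|---|
| 0% | 5.0% | 5.3% |
| 2% | 5.5% | 5.8-5.9% |
| 5% | 6.3% | 6.7-6.8% |
| 10% | 7.9-8.0% | 8.4-8.6% |
| 20% | 12.5-12.7% | 13.5-13.8% |

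At 20% loss, the Farrington-Manning test gives 12.3-12.5%. A posterior probability above 95%, which is the decision rule in Section 5, gives 13.1-13.3%. The SAP states no prior; flat and Jeffreys priors were assumed and agree. The range over methods is 12-14%.

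**3. Followed subjects only.** With 250 × (1 − d) per arm and unshrunk rates, the exact error stays at about 5.3-5.5% for losses up to 20%.

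**4. Sensitivity to the assumptions.**

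- Half of the lost subjects' events recorded, 20% loss: 7.8-8.6%.
- Loss of 20% in the Test arm only: about 27%.
- Loss of 20% in Control only: about 1.5-1.7%, so the direction reverses.
- Smaller trial (assumed n, since actual enrolment is not given), exact test, 20% equal loss: 10.9-11.2% at 100 per arm against 5.8-5.9% with no loss; 9.5-9.6% at 50 per arm against 6.2%.

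**The case against.** **Does the rule reach MACE?** The Section 9 sentence is introduced as a summary of site-reported adverse events. MACE is adjudicated (Section 13 lists the adjudication results), and its decision rule is the posterior probability in Section 5. Applying the whole-set denominator to the non-inferiority decision is therefore an inference. This stands as a limit. But Section 9 names MACE, notes no exception, and no other section supplies a rule.

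**Does the plan already secure follow-up?** Section 6.2 says that subjects in the safety set will be confirmed as followed for 12 months, Section 6.1 waits for all follow-ups, and Section 7.1 tabulates those reaching day 30. Section 6.1 also excepts subjects lost to follow-up, and nothing says how to count them.

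**Is the size exaggerated?** A reader might infer that the plan's own 20% drop-out raises the error to about 14%. The SAP does not support that. It never says that the 20% falls before day 30. Where the figure appears for safety, lost subjects are removed, which is the sounder handling. The same 20% heads Table 3, which sizes the cMR endpoint, and a subject without a cMR can still be followed for MACE. Adverse events are collected from the procedure onward (Section 4.4), so some events before loss would be recorded. The trial also stopped short of full enrolment (Section 6.4), so 250 per arm will not be analysed. A reader might also infer that the bias always favours the device; loss mainly in Control does the opposite.

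**Is a whole-set denominator wrong in itself?** For descriptive adverse-event tables it is a common convention and can stay.

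**Conclusion.** The concern holds as a contradiction over the denominator of the primary safety endpoint, together with a missing rule for unknown 30-day status. Section 9, the more specific text, is the reading that produces bias. With similar loss in both arms, or more in the Test arm, that bias is towards non-inferiority.

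The size depends on loss before day 30, which the SAP does not give. Under the worst-case recording assumption at 250 per arm, the error is about 5% with no loss, 6-7% at 5%, 8-9% at 10% and 12-14% at 20%; at an assumed 100 per arm it is about 11% at 20%. If loss before day 30 is only a few per cent and balanced, the inflation is small. The need for one rule does not depend on which of these applies.

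**What to change.** - For the 30-day MACE non-inferiority analysis, define the denominator as subjects with a MACE by day 30 or with follow-up to day 30, and state how a visit earlier than day 30 but inside the ±7-day window counts. Kaplan-Meier day-30 rates with an interval for their difference are an alternative; they also use the time at risk of subjects who leave early.
- Reconcile Sections 5, 7, 9 and 9.1 to that rule, and say explicitly that it governs the non-inferiority decision.
- Add one sensitivity analysis for subjects with unknown 30-day status, for example assigning lost Test subjects the control rate plus 6 points. Report the number with unknown status by arm.
- Keep the whole-set denominator for descriptive adverse-event tables if wanted, labelled as such.

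The cost is SAP wording and minor programming, plus a slightly wider interval for the MACE difference. Section 2 places finalisation of the SAP before database lock, and the rule should be fixed by then.

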3.1 Study Objectives

This is a confirmatory trial to evaluate safety and effectiveness of therapeutic hypothermia using ZOLL Proteus IVTM System for patients with acute anterior MI in comparison with anterior MI patients who only undergo PCI. Efficacy is established by demonstrating a relative reduction of 20% in mean anterior myocardial infarct size (IS), as determined by Cardiac Magnetic Resonance (cMR) imaging at 4-6 days post infarct in the Test Arm (cooling + PCI) compared to the Control Arm (PCI only). Infarction Size (IS) is defined as % Left Ventricular Mass as measured by Cardiac Magnetic Resonance (cMR) imaging.

Infarct Size (IS) will be assessed by Cardiac Magnetic Resonance (cMR) at 4 – 6 days following the index procedure and is a measurement of “myocardial reperfusion injury” by a Core Lab.

The trial is considered to have met the primary efficacy endpoint if the Test Arm demonstrates a 20% relative reduction in mean infarct size (defined as a 3.5% absolute reduction) compared to the Control Arm.

Furthermore, safety will be evaluated throughout the trial on basis of non-inferiority, with 6% established as the margin of non-inferiority.

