Table 1: Clinical trials reporting anterior mean infarct size measured by cMR 4-6 days in PCI trials (Control Group Only) and calculated 20% relative reduction

Study name	Anterior n	Mean infarct size	Standard Deviation	20% relative reduction
APEX-AMI³⁷	60	16.6	10.7	3.3
LIPSIAABCIXIMAB³⁸	63	25.3	16.1	5.1
LIPSIA-STEMI³⁹	38	18	16.0	3.6
CRISP-AMI^{40*}	142	37.5	20.1	7.5
INFUSE-AMI⁴¹	172	17.3	10.2	3.5
RAPID-MI ICE¹	7	19.7	8.5	3.9
CHILL-MI³³	21	26.5	10.9	5.3
AMI EU PILOT	21	23.3	12.0	4

*>60% are large proximal infarcts

COPY

Table 2: Hypothermia trials using cMR measured infarct size as primary outcome

	RAPID-MI ICE (2009)	CHILL-MI (2013)	AMI EU Pilot (2017)	Pooled AMI EU Pilot, RAPID-MI-ICE, CHILL-MI
n (Control vs Cooled)	7 vs 5	21 vs 15	21 vs 19	49 vs 39
Control Mean LV%	19.7	26.5	23.3	24.5
20% reduction in infarct	3.94	5.3	4.7	4.9
Std Dev (control)	8.5	10.9	12.0	10.5
Std Dev (cooled)	6.5	9.3	10.3	11.0

The potential impact of variations in control infarct size and variability is presented in **Table 3**.

Table 3: Sample size estimates with alternative standard deviation and detection limit

Mean Difference in infarct size for detection (%)	Standard Deviation	Estimated Sample Size	Total Enrolment (with 20% drop-out)
3.0	9	288	360
3.0	10	355	444
3.0	11	430	534
3.0	12	506	636
3.5	9	212	264
3.5	10	260	330
3.5	11	314	396
3.5	12	374	468
4.0	9	162	204
4.0	10	200	252
4.0	11	240	300
4.0	12	286	360

The safety endpoint is a composite endpoint. In consideration regarding power of this study, expected incidence is based on a literature review of acute MI hypothermia trials that combined six studies: Dixon et al, COOL MI, ICE-IT, RAPID MI-ICE, CHILL-MI, VELOCITY¹¹ which resulted in a 30-day MACE rate of 6.6% in the Control patients and 7.5% in treatment patients. Previously, AMIHOT II trial defined 30-day MACE rate comprised of death, reinfarction, target vessel revascularization, and stroke used a non-inferiority hypothesis with a 6% equivalence delta and 7% in the Control patients¹².

The hypothesis for the primary safety endpoint is the following:

$$H_0: \pi_T \geq \pi_C + 6\%$$

$$H_A: \pi_T < \pi_C + 6\%$$

π_T and π_C are the underlying proportion of patients having a MACE event.

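### The analysis sections do not carry out the 6-point non-inferiority rule for 30-day MACE: the only test they name ignores the margin, and the Section 5 posterior rule has no prior or model

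*SAP*

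**What the plan says.** The objective is stated in SAP Section 3.1, "with 6% established as the margin of non-inferiority", and Section 3.2 lists 30-day MACE as the primary safety endpoint, tested for non-inferiority to Control.

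Section 5 (Sample Size) writes out the hypotheses under "The hypothesis for the primary safety endpoint is the following": the null is that the Test rate is at least the Control rate plus 6 points. It then gives the decision rule: "The safety endpoint will be considered to have been met if there is a high posterior probability of non-inferiority", with a threshold of 95%. It names no prior, likelihood or computation, and nor does any other section.

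Section 6.7 covers the same endpoint. It opens "For primary and secondary safety analyses, given the number of statistical tests" and ends "Tests will be conducted using one-sided test at alpha 0.05 level of significance". It mentions neither the margin nor a posterior probability.

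Section 9 (Safety Analyses) names one family of tests: "1-sided Chi-square test or Fisher’s-exact test will be used as appropriate depending on whether number of patients are fewer than 5". It continues "Only deviations from the aforementioned analytical and summary approaches will be noted in the subsequent subsections of section 9" and then "The only summarized variable is MACE, which is also a composite endpoint". Sections 9.1 to 9.4 give no separate method for MACE.

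In Section 13, the table row for MACE as primary safety asks for a count with percentage and a p-value. It has no rate difference, confidence limit or posterior probability.

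**The concern.** A standard chi-square or Fisher test asks whether the two MACE rates are equal. Section 5 asks whether the Test rate exceeds the Control rate by less than 6 points. These are different hypotheses, and a p-value for the first does not in general answer the second. A significantly lower Test rate would imply non-inferiority, but any other result leaves the question open. Section 9 does not even say which direction its one-sided test takes.

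The plan thus holds one rule that addresses the right hypothesis but cannot be run as written, and one named test that can be run but addresses another hypothesis. This is one of two primary endpoints in a trial that Section 3.1 calls confirmatory. The trial is open-label, and Section 6.4 records that it never reached full enrolment. If the rule is not fixed in advance, the safety conclusion could depend on which one is picked once the counts are known.

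**Working it through.** **Inputs from the SAP.** Margin 6 points, one-sided alpha 0.05, posterior threshold 95%, 250 per arm planned, 200 per arm with Section 5's 20% dropout, literature MACE rates 6.6% (Control) and 7.5% (Test), and a 7% Control rate from the earlier trial that Section 5 cites.

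**Assumptions.** Independent Beta(1,1) priors, because the SAP gives none; Fisher's test when either arm has fewer than 5 events; 17 Control events out of 250 (6.8%) as a worked case. Final enrolment is not stated, so planned sizes are used.

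**The plan's own power figure.** Section 5 states 91% at 500 subjects and 86% with 20% dropout. Power = Φ{[0.06 − (pT − pC)]/SE − 1.645}, with SE = √[pC(1−pC)/n + pT(1−pT)/n]. At 6.6% and 7.5% this gives 72.0% (250 per arm) and 63.6% (200 per arm). At 7% in both arms it gives 83.8% and 76.0%. The stated pair does not follow from the stated inputs. That is a separate matter, but it means the power statement does not reveal which method was intended.

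**Formulas for the worked case (n = 250 per arm).**
- Equality test: z = (pT − pC)/√[2p(1−p)/n], where p is the pooled rate.
- Wald one-sided 95% upper limit: (pT − pC) + 1.645·SE.
- Miettinen-Nurminen limit: the difference d at which the score statistic, with variances constrained to d, equals −1.645.
- Section 5 rule: P(πT < πC + 0.06) by numerical integration over the two beta posteriors.

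*19 Test events.* Difference 2/250 = 0.8 points; pooled rate 36/500 = 0.072; z = 0.008/0.02312 = 0.35, so p = 0.64 for Test lower. Wald limit 0.008 + 1.645 × 0.02312 = 4.6 points. Posterior 0.986. Section 5 is met, while the named test shows nothing.

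*27 Test events.* Difference 10/250 = 4 points; pooled rate 44/500 = 0.088; z = 0.04/0.02534 = 1.58, so p = 0.057 for Test higher. Wald limit 0.04 + 1.645 × 0.02528 = 8.2 points. Posterior 0.79. Section 5 fails, while the table would show a non-significant p-value.

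**Across Test counts, with 17 Control events.**

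| Test events | Equality test | Section 5 posterior |
|---|---|---|
| 4–8 | Test significantly lower | met |
| 9–22 | Test lower not significant (p = 0.0535 to 0.80) | met (0.950 or higher) |
| 23–27 | Test higher not significant (p = 0.161 to 0.057) | not met (0.93 to 0.79) |
| 28–29 | Test significantly higher | not met |

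For 27 − 9 + 1 = 19 consecutive counts the p-value does not settle the Section 5 question.

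**Operating characteristics (exact binomial sums over all outcomes).**

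| True rates, Control / Test | Result | 250 per arm | 200 per arm |
|---|---|---|---|
| 6.6% / 7.5% | Test significantly lower | 2.1% | 2.3% |
| 6.6% / 7.5% | posterior rule met | 72% | 63% |
| 6.6% / 7.5% | Miettinen-Nurminen limit below 6 points | 70% | 62% |
| 7% / 13% (at the margin) | excess not significant | 27% | 36% |
| 7% / 13% | posterior rule met | 5.3% | 5.3% |
| 7% / 13% | Miettinen-Nurminen limit below 6 points | 4.9% | 4.9% |

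The 27% and 36% become false acceptances only if a non-significant excess is read as non-inferiority. The SAP does not say that it would be.

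**Why the method must be named.** At 17 against 22 events the posterior is 0.9503 (met), the Wald limit is 0.02 + 1.645 × 0.02397 = 5.94 points (met), and the Miettinen-Nurminen limit is 6.08 points (not met).

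**The case against.** The best defence is that Section 5 already fixes the margin, hypotheses and threshold, and that no sentence says a chi-square or Fisher p-value decides safety. Section 9 opens with site-reported adverse events, so its test may be meant only for those. The one-sided 0.05 in Section 6.7 is compatible with a margin test, and the table's unnamed p-value could be a non-inferiority p-value. That reading is possible. On it, however, no analysis section describes the primary safety analysis, the p-value comes from no identified test, and the posterior rule still cannot be run. On the other reading the wrong hypothesis is tested. Both need correction, and Section 9's default rule followed by its MACE sentence favours the second.

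Several limits stand. In the middle range the equality test is inconclusive; it does not contradict Section 5. The disagreement is between meeting one criterion and not meeting the other. The missing prior matters little if vague: Beta(0.5,0.5) gives the same verdict as Beta(1,1) at every Test count from 4 to 29, and power shifts by about 1 point at most. The 17 against 22 case is a single boundary count. The figures describe the planned sizes, not the sample actually reached.

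**Conclusion.** The concern holds and should be corrected before the safety analysis is run. The missing margin is the substantive fault, because it changes the conclusion over a wide range of plausible results: 19 consecutive Test counts in the worked case, and 2.1% against 72% for meeting the criterion at the plan's literature rates with 250 per arm. The missing prior and model is a lesser, but real, gap in pre-specification. The numerical results rest on assumed Beta(1,1) priors, planned arm sizes and 17 Control events as the example. The mismatch between Section 5 and Sections 9 and 13 does not depend on those choices.

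**What to change.** State one margin-based rule for primary safety and repeat it in Section 6.7, Section 9 and the MACE row of Section 13. There are two acceptable forms:

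- the one-sided 95% upper score limit for the Test-minus-Control difference lies below 6 points, with the method named (Miettinen-Nurminen or Farrington-Manning); or
- the Section 5 posterior rule, with its prior and model written out.

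Report the difference with that limit or probability in the MACE table. Restrict chi-square and Fisher tests to other adverse events and state their direction.

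The cost is SAP wording and a few lines of code, with no new data. With fewer subjects than planned, a margin-based rule is less likely to be met (72% at 250 per arm, 63% at 200 per arm, at the literature rates). That reflects the information lost by stopping early, and a p-value from an equality test does not restore it.
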